#### Data structure and parameter of interest

Consider a survival distribution involving iid data units  $(Y, \Delta, Z)$ , in which  $Y \equiv \min\{T, C\}$  is the observed minimum of failure and right-censoring time,  $\Delta \equiv I\{T \leq C\}$  is the event indicator, and Z = (W, A) is a vector of covariates. However, we assume a two-phase sampling structure in which we

instead observe a coarsened version of this data structure in which we first observe  $(Y_1, \Delta_1, W_1), ..., (Y_n, \Delta_n, W_n) \stackrel{iid}{\sim} P_0$ . We then construct a set of indicator variables  $R_1, ..., R_n$  based on our "phase 1 sample" and observe the variable  $A_i$  for subject *i* if  $R_i = 1$ . Different methods exist to construct the indicators  $R_1, ..., R_n$ , but we will assume that  $R_i \sim \text{Bernoulli}(\pi_0(Y_i, \Delta_i, W_i))$ for a known function  $\pi_0$ . Importantly, the weights partition the observations into a finite set of strata  $\{1, ..., J\}$  such that *i* and *j* are in the same stratum if and only if  $\pi_0(Y_i, \Delta_i, W_i) = \pi_0(Y_j, \Delta_j, W_j)$ ; this is one way to define twophase sampling (Breslow et al., 2009a, 2009b). Let  $C_i$  denote the index of the stratum to which observation *i* belongs. This yields a coarsened observed data structure that can be summarized as follows (where  $P_0$  is redefined to include the additional variables):

$$\mathcal{O}_1, ..., \mathcal{O}_n \equiv (Y_1, \Delta_1, W_1, R_1, R_1, A_1, C_1), ..., (Y_n, \Delta_n, W_n, R_n, R_n, A_n, C_n) \stackrel{iid}{\sim} P_0.$$

For a fixed time t, the parameter of interest is the g-computed survival curve defined as follows, where  $S_0(t|w, a) = P(T > t|W = w, A = a)$  is the true conditional survival function:

$$a \mapsto \overline{S}_0(t|a) \equiv E_0[S_0(t|W,a)].$$

Our goal is to use the coarsened data structure to make pointwise inference about  $\bar{S}_0(t|a)$  for a fixed value a. We proceed by assuming that the true full-data distribution follows a Cox model and fitting an inverse-probabilitysampling weighted Cox model to estimate the conditional survival function  $S_n$ . We then marginalize over the observed covariates, yielding the following estimator, where  $\beta_n$  is the estimator of the Cox model parameter vector  $\beta_0$ and  $\Lambda_n$  is the inverse probability sampling weighted version of the so-called Breslow estimator of the baseline cumulative hazard function  $\Lambda_0$ :

$$\bar{S}_n(t|a) \equiv \sum_{i=1}^n S_n(t|w_i, a) = \sum_{i=1}^n exp\left(-e^{(w_i, a)'\beta_n}\Lambda_n(t)\right)$$

Our strategy for estimating Var  $(\bar{S}_n(t|a))$  will be to derive the influence functions of  $\beta_n$  and  $\Lambda_n(t)$ , apply the delta method to find the influence function of  $S_n(t|w, a)$  for fixed w, and then account for the marginalization to derive the influence function of  $\bar{S}_n(t|a)$ .

#### Inverse probability sampling weighting using estimated weights

Inverse probability sampling (IPS) weighting allows us to identify various quantities of interest in terms of the observed data structure. Although IPS weighting based on the true weights  $\pi_i \equiv \pi_0(y_i, \delta_i, w_i)$  can be used, we can gain efficiency by using the following estimated weights:

$$\pi_i^* \equiv \pi_n^*(o_i) \equiv \frac{\sum_{j=1}^n I\{c_i = c_j\}r_j}{\sum_{j=1}^n I\{c_i = c_j\}}.$$

The denominator in the expression above represents the number of observations in stratum  $c_i$  (the stratum to which observation *i* belongs) and the denominator represents the number of observations in stratum  $c_i$  selected in the phase-two sample.

For a fixed function h, we will need to repeatedly use IPS weighting to estimate terms of the form  $E_0[h(\mathcal{O})]$  using the IPS-weighted estimator  $n^{-1}\sum_{i=1}^n (r_i/\pi_i^*)h(o_i)$ . However, this estimator is not asymptotically linear, since the  $\pi_i^*$  terms depend on the entire sample within a given stratum. Therefore, we will make use of the following equality, which can be derived using the delta method and holds under mild regularity conditions, where  $p_0(c) \equiv P_0(C = c)$  and  $p_0^1(c) \equiv P_0(C = c, R = 1)$ :

$$\frac{1}{n}\sum_{i=1}^{n}\frac{r_{i}}{\pi_{i}^{*}}h(o_{i}) = \frac{1}{n}\sum_{i=1}^{n}\left(\frac{r_{i}}{\pi_{i}}h(o_{i}) + \left(1 - \frac{p_{0}(c_{i})r_{i}}{p_{0}^{1}(c_{i})}\right)E_{0}\left[h(\mathcal{O})\left|C = c_{i}, R = 1\right]\right) + o_{P_{0}}(n^{-1/2}).$$
(3)

#### Influence function of $\beta_n$

The full-data influence function of the Cox model is given by  $\tilde{\ell}_0 \equiv \mathcal{I}_0^{-1} \ell_0^*$ , where  $\mathcal{I}_0$  is the efficient information and  $\ell_0^*$  is the efficient score. To provide expressions for these quantities, it is useful to first define the following expressions (where we use the notation  $X^{\otimes 2} \equiv XX'$ ):

$$S_{0}^{(0)}(x) \equiv E_{0} \left[ e^{Z'\beta_{0}} I\{Y \ge x\} \right]$$

$$S_{0}^{(1)}(x) \equiv E_{0} \left[ Z e^{Z'\beta_{0}} I\{Y \ge x\} \right]$$

$$S_{0}^{(2)}(x) \equiv E_{0} \left[ Z^{\otimes 2} e^{Z'\beta_{0}} I\{Y \ge x\} \right]$$

$$m_{0}(x) \equiv S_{0}^{(1)}(x) / S_{0}^{(0)}(x)$$

$$M_{i}(x) \equiv \delta_{i} I\{y_{i} \le x\} - e^{z_{i}'\beta_{0}} \int_{0}^{x} I\{y_{i} \ge u\} d\Lambda_{0}(u)$$

We can then define the efficient score and information as follows (note that we assume that Y is bounded above by  $\tau$ ):

$$\ell_0^*(z_i, \delta_i, y_i) \equiv \int_0^\tau (z_i - m_0(x)) \, dM_i(x)$$
$$\mathcal{I} \equiv E_0 \left[ e^{Z'\beta_0} \int_0^\tau (Z - m_0(x))^{\otimes 2} \, I\{Y \ge x\} d\Lambda_0(x). \right]$$

According to equation (19) of Breslow and Wellner (2007) the following equality holds, given mild regularity conditions:

$$\beta_n - \beta_0 = \frac{1}{n} \sum_{i=1}^n \frac{r_i}{\pi_i^*} \tilde{\ell}_0(o_i) + o_{P_0}(n^{-1/2}).$$

Applying (3) to this equation, we can write the following:

$$\beta_n - \beta_0 = \frac{1}{n} \sum_{i=1}^n \left( \frac{r_i}{\pi_i} \tilde{\ell}_0(o_i) + \left( 1 - \frac{p_0(c_i)r_i}{p_0^1(c_i)} \right) E_0 \left[ \tilde{\ell}_0(\mathcal{O}) \left| C = c_i, R = 1 \right] \right) + o_{P_0}(n^{-1/2})$$

Thus, the influence function of  $\beta_n$  under two-phase sampling with estimated weights is given by:

$$\tilde{\ell}_{0}^{*}: o_{i} \mapsto \frac{r_{i}}{\pi_{i}} \tilde{\ell}_{0}(o_{i}) + \left(1 - \frac{p_{0}(c_{i})r_{i}}{p_{0}^{1}(c_{i})}\right) E_{0}\left[\tilde{\ell}_{0}(\mathcal{O}) | C = c_{i}, R = 1\right].$$
(4)

#### Influence function of $\Lambda_n$

The IPS-weighted Breslow estimator is given by the following:

$$\Lambda_n(t) \equiv \sum_{\{i:\delta_i=1\}} \frac{(r_i/\pi_i^*)I\{y_i \le t\}}{\sum_{j=1}^n (r_j/\pi_j^*)I\{y_j \ge y_i\}e^{z'_j\beta_n}}.$$

To study this estimator, we first define the following:

$$S_{0}^{(0)}(x,\beta) \equiv E_{0}[e^{Z'\beta}I\{Y \ge x\}]$$

$$S_{n}^{(0)}(x,\beta) \equiv \sum_{i=1}^{n} \frac{r_{i}}{\pi_{i}^{*}}e^{z_{i}'\beta}I\{y_{i} \ge x\}$$

$$F_{1,0}(x) \equiv P_{0}(Y \le x, \Delta = 1)$$

$$F_{1,n}(x) \equiv \sum_{i=1}^{n} \frac{r_{i}}{\pi_{i}^{*}}\delta_{i}I\{y_{i} \le x\}$$

$$\Lambda_{0}(t,\beta) \equiv \int_{0}^{t} \frac{dF_{1,0}(x)}{S_{0}^{(0)}(x,\beta)}$$

$$\Lambda_{n}(t,\beta) \equiv \int_{0}^{t} \frac{dF_{1,n}(x)}{S_{n}^{(0)}(x,\beta)}.$$

It can be shown that  $\Lambda_0(t, \beta_0)$  is equal to the baseline cumulative hazard function  $\Lambda_0(t)$  and  $\Lambda_n(t, \beta_n)$  is equal to the IPS-weighted Breslow estimator  $\Lambda_n(t)$ . Also note that  $S_0^{(0)}(x, \beta_0) = S_0^{(0)}(x)$ . We will study the asymptotic behavior of  $\Lambda_n(t)$  using the following expansion, which holds given mild regularity conditions:

$$\begin{split} \Lambda_n(t) - \Lambda_0(t) &= \Lambda_n(t, \beta_n) - \Lambda_0(t, \beta_0) \\ &= (\Lambda_n(t, \beta_0) - \Lambda_0(t, \beta_0)) + (\Lambda_0(t, \beta_n) - \Lambda_0(t, \beta_0)) + o_{P_0}(n^{-1/2}) \\ &= (\Lambda_n(t, \beta_0) - \Lambda_0(t, \beta_0)) + \left( \left. \frac{\partial}{\partial \beta} \Lambda_0(t, \beta) \right|_{\beta = \beta_0} \right) (\beta_n - \beta_0) + o_{P_0}(n^{-1/2}). \end{split}$$

Defining  $\mu_0(t) \equiv \left. \frac{\partial}{\partial \beta} \Lambda_0(t,\beta) \right|_{\beta=\beta_0} = \int_0^t m_0(x) d\Lambda_0(x)$ , this expansion can be expressed as:

$$\Lambda_n(t) - \Lambda_0(t) = (\Lambda_n(t,\beta_0) - \Lambda_0(t,\beta_0)) + \mu_0(t)(\beta_n - \beta_0) + o_{P_0}(n^{-1/2}).$$
(5)

Next, we study the asymptotic behavior of  $\Lambda_n(t, \beta_0)$  through the following expansion:

$$\Lambda_n(t,\beta_0) - \Lambda_0(t,\beta_0) = \left(\int_0^t \frac{dF_{1,n}(x)}{S_n^{(0)}(x,\beta)} - \int_0^t \frac{dF_{1,n}(x)}{S_0^{(0)}(x,\beta)}\right) + \left(\int_0^t \frac{dF_{1,n}(x)}{S_0^{(0)}(x,\beta)} - \int_0^t \frac{dF_{1,0}(x)}{S_0^{(0)}(x,\beta)}\right).$$
 (6)

To study this expansion, we first apply result (3) to both  $S_n^{(0)}(x,\beta)$  and  $F_{1,n}(x)$  to obtain the following:

$$S_n^{(0)}(x,\beta) = \frac{1}{n} \sum_{i=1}^n \left( \frac{r_i}{\pi_i} I\{y_i \ge x\} e^{z_i'\beta} + \left( 1 - \frac{p_0(c_i)r_i}{p_0^1(c_i)} \right) E_0 \left[ I\{Y \ge x\} e^{Z'\beta} \, | C = c_i, R = 1 \right] \right) + o_{P_0}(n^{-1/2})$$

$$\tag{7}$$

$$F_{1,n}(x) = \frac{1}{n} \sum_{i=1}^{n} \left( \frac{r_i}{\pi_i} \delta_i I\{y_i \le x\} + \left( 1 - \frac{p_0(c_i)r_i}{p_0^1(c_i)} \right) E_0\left[\Delta I\{Y \le x\} | C = c_i, R = 1\right] \right) + o_{P_0}(n^{-1/2}).$$
(8)

Define the following function for convenience:

$$\nu_0(o_i, x, \beta) \equiv \left(1 - \frac{p_0(c_i)r_i}{p_0^1(c_i)}\right) E_0\left[I\{Y \ge x\}e^{Z'\beta} | C = c_i, R = 1\right].$$

Using the delta method, we can write the following, where in the last line we have implicitly pulled out several second-order terms when substituting  $dF_{1,0}$  for  $dF_{1,n}$ :

$$S_{n}^{(0)}(x,\beta) - S_{0}^{(0)}(x,\beta) = \frac{1}{n} \sum_{i=1}^{n} \left( \frac{r_{i}}{\pi_{i}} I\{y_{i} \ge x\} e^{z_{i}'\beta} + \nu_{0}(o_{i},x,\beta) - S_{0}(x,\beta) \right) + o_{P_{0}}(n^{-1/2})$$

$$\frac{1}{S_{n}^{(0)}(x,\beta)} - \frac{1}{S_{0}^{(0)}(x,\beta)} = \frac{1}{n} \sum_{i=1}^{n} \frac{S_{0}(x,\beta) - (r_{i}/\pi_{i})I\{y_{i} \ge x\} e^{z_{i}'\beta} - \nu_{0}(o_{i},x,\beta)}{(S_{0}(x\beta))^{2}} + o_{P_{0}}(n^{-1/2})$$

$$\int_{0}^{t} \frac{dF_{1,n}(x)}{S_{n}^{(0)}(x,\beta)} - \int_{0}^{t} \frac{dF_{1,n}(x)}{S_{0}^{(0)}(x,\beta)} = \int_{0}^{t} \frac{S_{0}(x,\beta) - \frac{1}{n} \sum_{i=1}^{n} \left( (r_{i}/\pi_{i})I\{y_{i} \ge x\} e^{z_{i}'\beta} - \nu_{0}(o_{i},x,\beta) \right)}{(S_{0}(x\beta))^{2}} dF_{1,0}(x) + o_{P_{0}}(n^{-1/2})$$

Next, we define the following for convenience:

$$\nu_0^*(o_i, t, \beta) \equiv \left(1 - \frac{p_0(c_i)r_i}{p_0^1(c_i)}\right) E_0\left[\frac{\Delta I\{Y \le t\}}{S_0(Y, \beta)} | C = c_i, R = 1\right].$$

This allows us to write the following:

$$F_{1,n}(x) - F_{1,0}(x) = \frac{1}{n} \sum_{i=1}^{n} \left( \frac{r_i}{\pi_i} \delta_i I\{y_i \le x\} + \left(1 - \frac{p_0(c_i)r_i}{p_0^1(c_i)}\right) E_0\left[\Delta I\{Y \le x\} | C = c_i, R = 1\right] - F_{1,0}(x) \right) + o_{P_0}(n^{-1/2})$$

$$\int_0^t \frac{d(F_{1,n} - F_{1,0})(x)}{S_0(x,\beta)} = \frac{1}{n} \sum_{i=1}^n \left( \frac{r_i \delta_i I\{y_i \le t\}}{\pi_i S_0(y_i,\beta)} + \nu_0^*(o_i,t,\beta) \right) - \Lambda_0(t,\beta) + o_{P_0}(n^{-1/2}).$$

Combining this with the previous result, we have:

$$\Lambda_{n}(t,\beta) - \Lambda_{0}(t,\beta) = \frac{1}{n} \sum_{i=1}^{n} \left( \frac{r_{i} \delta_{i} I\{y_{i} \leq t\}}{\pi_{i} S_{0}(y_{i},\beta)} + \nu_{0}^{*}(o_{i},t,\beta) - \int_{0}^{t} \left( \frac{r_{i} I\{y_{i} \geq x\} e^{z_{i}'\beta} + \pi_{i} \nu_{0}(o_{i},x,\beta)}{\pi_{i} \left(S_{0}(x,\beta)\right)^{2}} \right) dF_{1,0}(x) \right) + o_{P_{0}}(n^{-1/2}).$$
(9)

Returning to the expansion given in (6) and plugging in these equalities, we can write the following:

$$\Lambda_n(t) - \Lambda_0(t) = \frac{1}{n} \sum_{i=1}^n \left( \frac{r_i \delta_i I\{y_i \le t\}}{\pi_i S_0(y_i)} + \nu_0^*(o_i, t, \beta_0) - \int_0^t \left( \frac{r_i I\{y_i \ge x\} e^{z'_i \beta_0} + \pi_i \nu_0(o_i, x, \beta_0)}{\pi_i \left(S_0(x)\right)^2} \right) dF_{1,0}(x) - \mu_0(t) \tilde{\ell}_0^*(o_i) \right) + o_{P_0}(n^{-1/2}).$$

Using the above and the equality  $\int_0^t h(x) d\Lambda_0(x) = \int_0^t (h(x)/S_0^{(0)}(x)) dF_{1,0}(x)$ , we can write the influence function of the IPS-weighted Breslow estimator as follows:

$$\varphi_0^{\Lambda}: o_i \mapsto \frac{r_i \delta_i I\{y_i \le t\}}{\pi_i S_0(y_i)} + \nu_0^*(o_i, t, \beta_0) - \int_0^t \left(\frac{r_i I\{y_i \ge x\} e^{z'_i \beta_0} + \pi_i \nu_0(o_i, x, \beta_0)}{\pi_i S_0(x)}\right) d\Lambda_0(x) - \mu_0(t) \tilde{\ell}_0^*(o_i).$$
(10)

### Influence function of $\bar{S}_n(t|a)$

Using several applications of the delta method on the influence functions given by equations (4) and (10), we can write the following, where z is a fixed covariate vector:

$$S_n(t|z) - S_0(t|z) \equiv e^{z'\beta_n} \Lambda_n(t) - e^{z'\beta_0} \Lambda_0(t)$$
  
=  $-\frac{1}{n} \sum_{i=1}^n S_0(t|z) \left( \Lambda_0(t) e^{z'\beta_0} z' \tilde{\ell}_0^*(o_i) + e^{z'\beta_0} \varphi_0^{\Lambda}(o_i) \right) + o_{P_0}(n^{-1/2}).$ 

Thus, the influence function of  $S_n(t|z)$  is given by the following:

$$\omega_0^t: (o_i, z) \mapsto -S_0(t|z) \left( \Lambda_0(t) e^{z'\beta_0} z' \tilde{\ell}_0^*(o_i) + e^{z'\beta_0} \varphi_0^{\Lambda}(o_i) \right).$$
(11)

Next, we can study the asymptotic behavior of  $\overline{S}_n(t|a)$  through the following expansion, where we use the notation  $Pf \equiv E_P[f(\mathcal{O})]$  for a given probability measure P:

$$\bar{S}_n(t|a) - \bar{S}_0(t|a) = P_n S_n - P_0 S_0 = (P_n - P_0) S_0 + P_0 (S_n - S_0) + (P_n - P_0) (S_n - S_0).$$
(12)

The first term is linear and can be written as follows:

$$(P_n - P_0)S_0 = \frac{1}{n} \sum_{i=1}^n \left( S_0(t|w_i, a) - E_0[S_0(t|W, a)] \right).$$
(13)

The second term can be represented as follows, which holds under mild regularity conditions on the remainder:

$$P_0(S_n - S_0) = E_0[S_n(t|W, a) - S_0(t|W, a)] = \frac{1}{n} \sum_{i=1}^n E_0\left[\omega_0^t(o_i, (W, a))\right] + o_{P_0}(n^{-1/2}).$$
(14)

Plugging these two equalities into expansion (12) and assuming regularity conditions hold such that  $(P_n - P_0)(S_n - S_0) = o_{P_0}(n^{-1/2})$ , we can write the following:

$$\bar{S}_n(t|a) - \bar{S}_0(t|a) = \frac{1}{n} \sum_{i=1}^n \left( S_0(t|w_i, a) - E_0[S_0(t|W, a)] + E_0\left[\omega_0^t(o_i, (W, a))\right] \right) + o_{P_0}(n^{-1/2}).$$

Therefore, the influence function of  $\bar{S}_n(t|a)$  is given by:

$$\varphi_0^{t,a}: o_i \mapsto S_0(t|w_i, a) - E_0[S_0(t|W, a)] + E_0\left[\omega_0^t(o_i, (W, a))\right].$$
(15)

The variance of  $\bar{S}_n$  can be estimated by estimating the second moment of its influence function (15), as usual. However, since  $\bar{S}_n \in [0, 1]$ , it may be useful to form confidence intervals on the logit( $\bar{S}_n$ ) scale instead and then transform the confidence limits back to the  $\bar{S}_n$  scale, to ensure that the entire confidence interval lies within [0, 1]. This yields the following confidence interval estimator, where  $\xi(x) \equiv \text{logit}(x), \ \dot{\xi}(x) \equiv \frac{d}{dx} \text{logit}(x), \ \xi^{-1}(x) \equiv \text{expit}(x), \ Z_{\alpha/2}$  is the relevant quantile of the standard Normal distribution, and  $\varphi_n^{t,a}$  is an estimator of the true influence function  $\varphi_0^{t,a}$ , which we will define later:

$$\xi^{-1}\left(\xi(\bar{S}_n(t|a)) \pm Z_{\alpha/2}\dot{\xi}\left(\bar{S}_n(t|a)\right)\sqrt{\frac{1}{n}\sum_{i=1}^n \left(\varphi_0^{t,a}(o_i)\right)^2}\right).$$
 (16)

Estimation of the influence function of  $\beta_n$  under iid sampling:  $\tilde{\ell}_n$ First, we define the following component function estimators:

$$S_{n}^{(0)}(x) \equiv \frac{1}{n} \sum_{i=1}^{n} \frac{r_{i}}{\pi_{i}^{*}} I\{y_{i} \ge x\} e^{z_{i}^{\prime}\beta_{n}}$$

$$S_{n}^{(1)}(x) \equiv \frac{1}{n} \sum_{i=1}^{n} \frac{r_{i}}{\pi_{i}^{*}} z_{i} I\{y_{i} \ge x\} e^{z_{i}^{\prime}\beta_{n}}$$

$$S_{n}^{(2)}(x) \equiv \frac{1}{n} \sum_{i=1}^{n} \frac{r_{i}}{\pi_{i}^{*}} z_{i}^{\otimes 2} I\{y_{i} \ge x\} e^{z_{i}^{\prime}\beta_{n}}$$

$$m_{n}(x) \equiv S_{n}^{(1)}(x) / S_{n}^{(0)}(x).$$

We can then define our estimator as  $\tilde{\ell}_n \equiv \mathcal{I}_n^{-1} \tilde{\ell}_n^*$ , where  $\mathcal{I}_n$  and  $\tilde{\ell}_n^*$  are defined as follows:

$$\mathcal{I}_{n} \equiv \frac{1}{n} \sum_{\{i:\delta_{i}=1\}} \frac{r_{i}}{\pi_{i}^{*}} \left( \frac{S_{n}^{(2)}(y_{i})}{S_{n}^{(0)}(y_{i})} - (m_{n}(y_{i}))^{\otimes 2} \right)$$
$$\tilde{\ell}_{n}^{*} \equiv \delta_{i} \left( z_{i} - m_{n}(y_{i}) \right) - \sum_{\{j:\delta_{j}=1\}} \frac{r_{j}e^{z_{i}^{\prime}\beta_{n}}I\{y_{j} \leq y_{i}\}\left(z_{i} - m_{n}(y_{j})\right)}{\pi_{j}^{*}S_{n}^{(0)}(y_{j})}.$$

Estimation of the influence function of inverse probability sampling weighted  $\beta_n$  under two-phase sampling:  $\tilde{\ell}_n^*$ 

A consistent estimator of  $\tilde{\ell}_0^*$  is given by the following, where  $p_n(c) \equiv \frac{1}{n} \sum_{i=1}^n I\{c_i = c\}$  and  $p_n^1(c) \equiv \frac{1}{n} \sum_{i=1}^n I\{c_i = c\}r_i$ :

$$\tilde{\ell}_n^*(o_i) \equiv \frac{r_i}{\pi_i^*} \tilde{\ell}_n(o_i) + \frac{1}{n} \sum_{\{j:c_j=c_i,r_j=1\}} \frac{\left(p_n^1(c_j) - p_n(c_j)r_i\right)\tilde{\ell}_n(o_j)}{\left(p_n^1(c_j)\right)^2}$$

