#### 12.3.3 Univariable CoR: Marginalized Cox modeling

Time-to-event methods use the Day 57 visit date as the time origin.

The IPWCC Cox regression model designed for case-cohort sampling designs will be used for estimation and inference on hazard ratios of outcomes by Day 57 marker levels, and for estimation and inference on marginalized markerconditional cumulative incidence over time. The models will be fit using the *survey* R package available on CRAN, and will adjust for the baseline factors. We use a method from the survey package that assumes without replacement two-phase sampling and not Bernoulli sampling, which matches the sampling design and approach to weight estimation (Lumley, 2010).

For models with a single antibody marker, a two-phase Cox model with improved efficiency through calibrated weights (Breslow et al., 2009b,a) will be used if there are baseline covariates that predict the antibody marker with  $R^2 > 0.4$ . Based on the phase-two sample, a superlearner model will be fit (using the library specified in Table 7) to predict the antibody marker from the set of collected baseline covariates. The criterion  $R^2 > 0.4$  will be checked based on the association of the fitted values from superlearner and the marker, where the association uses held-out marker values.

Based on the Cox model fit to all available data during blinded follow-up (the period during which participants are blinded to randomization arm assignment), a final time point  $t_F$  near the time of the last observed outcome will be defined. Let T be the failure time, S a Day 57 marker of interest, and X the vector of baseline factors that are adjusted for. With  $S_1(t|s,x) = P(T > t|S = s, X = x, A = 1)$ , the Cox model fit yields an estimate of  $S_1(t|s, X_i)$  for each individual i in the phase-two sample. The marginalized conditional risk  $risk_1(t|s) = E_X[P(T \le t|s, X, A = 1)]$  through time t (for all times t through  $t_F$  simultaneously) is estimated based on the equation

$$risk_1(t|s) = \int (1 - S_1(t|s, x)) dH(x)$$
 (1)

where  $H(\cdot)$  is the distribution of X in A = 1 individuals.

The function  $risk_1(t|s)$  can be estimated by

$$\widehat{risk}_1(t|s) = \frac{1}{n} \sum_{i=1}^n (1 - \hat{S}_1(t|s, X_i)),$$
(2)

where n is the number of vaccine arm participants with phase-one data ( $X_i$  measured). The bootstrap is used to obtain 95% pointwise confidence intervals for  $risk_1(t_F|s)$ .

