## 12.3.4 Univariable CoR: Marginalized Cox modeling with influence-function based analytic variance estimation

The previous section described estimation and inference for  $risk_1(t|s)$  via the bootstrap. This section describes how to alternatively conduct inference via the influence function.

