# Estimation of the influence function of the IPS-weighted Breslow estimator: $\varphi_n^{\Lambda}$

The influence function  $\varphi_0^{\Lambda}$  can be consistently estimated using the following:

$$\varphi_n^{\Lambda}(o_i) \equiv \frac{r_i \delta_i I\{y_i \le t\}}{\pi_i^* S_n(y_i)} + \nu_n^*(o_i, t, \beta_n) - \frac{1}{n} \sum_{\{j:\delta_j=1\}} I\{y_j \le t\} \left(\frac{r_i I\{y_i \ge y_j\} e^{z_i'\beta_n} + \pi_i^* \nu_n(o_i, y_j, \beta_n)}{\pi_i^* \left(S_n(y_j)\right)^2}\right) - \mu_n(t) \tilde{\ell}_n^*(o_i).$$

This involves the following nuisance estimators:

$$\nu_n^*(o_i, t, \beta_n) \equiv \left(\frac{p_n^1(c_i) - p_n(c_i)r_i}{(p_n^1(c_i))^2}\right) \left(\frac{1}{n} \sum_{\{k:c_k = c_i, r_k = \delta_k = 1\}} \frac{I\{y_k \le t\}}{S_n(y_k)}\right)$$
$$\nu_n(o_i, y_j, \beta_n) \equiv \left(\frac{p_n^1(c_i) - p_n(c_i)r_i}{(p_n^1(c_i))^2}\right) \left(\frac{1}{n} \sum_{\{k:c_k = c_i, r_k = 1\}} I\{y_k \ge y_j\} e^{z'_k \beta_n}\right)$$
$$\mu_n(t) \equiv \frac{1}{n} \sum_{\{j:\delta_j = 1\}} \frac{I\{y_j \le t\} S_n^{(1)}(y_j)}{\left(S_n^{(0)}(y_j)\right)^2}.$$

Estimation of the influence function of conditional survival  $S_n(t|z)$ :  $\omega_0^t$ 

The influence function  $\omega_0^t$  can be consistently estimated using the following:

$$\omega_{n}^{t}(o_{i},z) \equiv e^{z'\beta_{n}} \left( \frac{\delta_{i}I\{y_{i} \leq t\}}{S_{n}^{(0)}(y_{i})} - \frac{1}{n} \sum_{\{j:\delta_{j}=1\}} \frac{e^{z_{i}'\beta_{n}I\{y_{j} \leq t \wedge y_{i}\}}}{\pi_{j}^{*} \left(S_{n}^{(0)}(y_{j})\right)^{2}} + \left( \frac{1}{n} \sum_{\{j:\delta_{j}=1\}} \frac{I\{y_{j} \leq t\}(z-m_{n}(y_{j}))}{\pi_{j}^{*}S_{n}^{(0)}(y_{j})} \right)' \tilde{\ell}_{n}(z_{i},\delta_{i},y_{i}) \right).$$

$$(17)$$

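### Section 12.3.4: the analytic confidence interval offered as an alternative to the bootstrap for the Cox marker-conditional risk curve is wrong as printed, with two missing divisions by n and a plug-in (eq. 17) that does not match eq. (11)

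*Combined protocol and SAP*

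**What the plan says.** Section 12.3.3 assigns the bootstrap to the risk curve: "The bootstrap is used to obtain 95% pointwise confidence intervals for" risk_1(t_F|s). Section 12.3.4 then adds an analytic route: "This section describes how to alternatively conduct inference via the influence function".

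Three places in Section 12.3.4 matter.

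- **Variance and interval.** Under the heading for the influence function of S̄_n(t|a), the variance "can be estimated by estimating the second moment of its influence function (15), as usual". The text then moves to the logit scale: "This yields the following confidence interval estimator", namely eq. (16), whose standard-error term is √((1/n) Σ φ²). Eq. (16) prints the true φ_0, although the sentence before it introduces an estimate φ_n.
- **Score plug-in for β_n.** S_n^(0) is defined there as an average, with 1/n in front. The compensator in the estimated score is a sum over events of r_j e^{z_i'β_n} I{y_j ≤ y_i}(z_i − m_n(y_j)) / (π_j* S_n^(0)(y_j)), with no 1/n.
- **Survival plug-in.** Under "Estimation of the influence function of conditional survival" S_n(t|z), eq. (17) is said to estimate consistently the influence function given in eq. (11).

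**The concern.** The expansion just above eq. (15) writes S̄_n minus its target as (1/n) times a sum of n influence terms. Its variance is therefore the second moment of the influence function divided by n. Neither the prose nor eq. (16) makes that division.

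The section also derives two-phase influence functions with care, in eqs. (4) and (10) and their plug-ins ℓ_n* and φ_n^Λ. Eq. (17) then uses neither.

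The Prelude invites other groups to implement the SAP or parts of it. Anyone coding this section as printed would get intervals that carry no information. Anyone repairing eq. (16) alone would still get them.

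**Working it through.** The SAP gives no numerical interval to reproduce, so the printed formulas were evaluated directly.

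**Inputs.** From the documents: 95% pointwise intervals (z = 1.96); at least 25 vaccine-arm cases for Cox CoR analyses and 50 for CoP (Table 4); 150 sampled in each of 6 baseline-negative vaccine strata (Table 5). Assumed, because the SAP gives no figure for this analysis: phase-one vaccine n and hence risk and, in the simulation, a marker hazard ratio of 0.5 per SD.

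**1. Eq. (16), closed form.** Without covariates or sampling, φ is approximately I(event) − p, with SD √(p(1−p)). The logit derivative is 1/(p(1−p)).

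- Printed half-width: 1.96·√(p(1−p))/(p(1−p)) = 1.96/√(p(1−p)), which does not depend on n.
- Correct half-width: the same divided by √n.

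At p = 0.5%: 1.96/√(0.005 × 0.995) = 27.8. Logit(0.005) = −5.29, so the printed interval runs from −33.1 to 22.5 on the logit scale, i.e. 4×10⁻¹⁵ to 1.000. With n = 5,000 (25 cases), 27.8/70.7 = 0.393, giving 0.34% to 0.74%.

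| Assumed n, cases | Risk | Eq. (16) as printed | Divided by √n |
|---|---|---|---|
| 14,000, 25 | 0.179% | 1×10⁻²³ to 1.000 | 0.121% to 0.264% |
| 14,000, 50 | 0.357% | 2×10⁻¹⁷ to 1.000 | 0.271% to 0.471% |
| 5,000, 25 | 0.50% | 4×10⁻¹⁵ to 1.000 | 0.34% to 0.74% |

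Even at 10% risk the printed interval is 0.02% to 98.7%.

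**2. Score plug-in.** With S_n^(0) an average, the Breslow jump at an event is (1/n)(r_j/π_j*)/S_n^(0)(y_j). The printed sum omits the 1/n, so the compensator is n times too large. In a full-cohort check with r = π = 1 (n = 3,000, 261 events), the SE of β was 0.068 with the 1/n, against a model SE of 0.064, and 83 as printed. That check does not test the two-phase design; the next one does.

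**3. Eq. (17) against eq. (11).** Eq. (11) is −S_0(t|z) e^{z'β_0} times (Λ_0(t) z'ℓ_0* + φ_0^Λ). Eq. (17) lacks the −S_n(t|z) factor and the r_i/π_i* weight on participant i, has no terms for estimated weights, and uses the iid score ℓ_n. Algebraically it is the complete-data influence function of the cumulative hazard e^{z'β}Λ(t). It needs e^{z_i'β_n}, marker included, for every phase-one participant, but the data-structure subsection says the marker is observed only if R_i = 1.

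**4. Simulation.** Weighted Cox fits to case-cohort data (6 × 150 plus all cases; n = 5,000 or 14,000; 19 to 123 cases; three marker values in each of four data sets). Results for n = 14,000, 35 cases, central marker value, estimated risk 0.227%:

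| Version | SE term | 95% interval |
|---|---|---|
| Correct two-phase φ, eq. (16) as printed | 0.0503 | 3×10⁻²² to 1.000 |
| Eq. (16) corrected, score as printed | 0.243 | 1×10⁻⁹⁴ to 1.000 |
| Eq. (16) and score scale corrected, eq. (17) in full-cohort form | 0.000424 | 0.157% to 0.327% |
| All corrected | 0.000425 | 0.157% to 0.327% |

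The first and last SEs differ by 0.0503/0.000425 = 118 = √14,000. With only eq. (16) repaired, all 12 settings gave a lower limit below 10⁻¹⁸ and an upper limit of 1.000. With both scalings repaired, the full-cohort eq. (17) gave an SE about 0% to 17% below the two-phase SE. The largest gap was at 123 cases and a low marker value: 0.00216 against 0.00259.

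Over 150 replicates with about 50 expected cases, the fully corrected SE averaged 0.00049 against an empirical SD of 0.00046 (central marker), and 0.00037 against 0.00036 (high marker). The full-cohort form averaged 0.00049 and 0.00036 there, so its understatement is not uniform.

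**The case against.** The strongest reply is that nothing named in the SAP depends on this interval. Section 12.3.3 assigns the bootstrap to the risk curve, Sections 12.3.5, 12.4 and 12.5.2 also use it, and the CoR p-values are Cox Wald tests. The controlled-risk sensitivity analysis (Section 15.1.1) cites Section 12.3.3. That stands, and it limits the severity.

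A second reply is that these are notation slips. The words as usual may imply the 1/n, and an exponent lost in PDF extraction cannot be excluded for eq. (16). But the sentence before it omits the division too, and the score error is separate.

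On the score, the subsection on Λ_n defines S_n^(0) as a plain sum, under which the printed compensator would be right. That does not rescue the section. The local definition carries 1/n, and the plug-ins φ_n^Λ and μ_n(t) combine explicit 1/n factors with S_n in the denominator, so they need the averaged version.

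The missing 1/n where S̄_n is first written as a sum is only notation: eq. (2) and eq. (12) both treat it as an average.

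Finally, an interval of 0% to 100% is conspicuous and could not support a false claim. The Prelude calls the SAP a work in progress, to be implemented on a mock data set. The code is not available here, so no reported interval is shown to be wrong.

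**Conclusion.** The concern holds for the printed formulas of Section 12.3.4. Two errors, the missing 1/n in eq. (16) and the missing 1/n in the score compensator, are each enough to give an interval of about 0% to 100% at any risk expected here. Eq. (17) is a third, separate fault: it cannot be computed under the sampling design and, once the scaling is right, tends to understate the SE by about 0% to 17% in the settings tried.

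Three stronger readings are tempting and not supported.

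- A reader might infer that the core CoR or controlled-risk results are compromised. They rest on Section 12.3.3.
- A reader might blame the full-cohort form of eq. (17) for the wide intervals. It does not widen them, and its missing −S_n(t|z) factor is almost harmless when survival is near 1.
- A reader might expect the printed interval to widen as n grows, because the inflation factor is √n. At fixed risk the correct SE shrinks at the same rate, so the printed half-width stays at 1.96/√(p(1−p)).

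The numbers rest on assumed n, risk and marker effect; the 0% to 100% result held at every value tried in the range of risks expected here. Severity: should-fix.

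**What to change.** 1. In eq. (16) use √((1/n²) Σ φ_n²), with the estimated φ_n^{t,a}, and state in the sentence before it that the second moment is divided by n.
2. Insert 1/n before the event sum in the score plug-in, and use one normalisation of S_n^(0) throughout Section 12.3.4.
3. Replace eq. (17) by the plug-in of eq. (11): ω_n = −S_n(t|z) e^{z'β_n} (Λ_n(t) z'ℓ_n*(o_i) + φ_n^Λ(o_i)), using the two-phase ℓ_n* and φ_n^Λ already given.
4. While there, weight the event sums in φ_n^Λ and μ_n(t) by r_j/π_j*. This matters if any case lacks marker data, which Section 12.3.1 allows for through the case weight N_1/n_1.
5. Add 1/n where S̄_n is first defined, for consistency.
6. Before use, compare the analytic SE with the Section 12.3.3 bootstrap on the mock data set.

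The cost is a handful of formula edits and one code check. No new data are needed and no estimand changes.
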